13.4.3. Studies of secondary objectives

- The evolution of the volume of lymphedema will be compared between the groups by repeated-time analysis of variance with two time factors and treatment with interaction on D5, DD + 30 and DD + 90.
- The frequency of patients whose lymphedema volume reduction is at least of 20% of the initial volume is described by numbers, frequencies, 95% confidence intervals and compared between groups by a Chi2 test at D5 and DD + 90.
- The percentage of patients for whom 70% of the initial benefit of the reduction of lymphedema obtained on day 5 is kept at DD + 90 at the end of the maintenance phase is described by number, frequency, 95% confidence interval and compared between groups by a Chi2 test at DD + 90.
- The improvement of the discomfort will be described through the CGII and the PGII (Patient Global Improvement Impression) by numbers, percentages and 95% confidence intervals and compared between groups by Wilcoxon rank tests. The evolutions within each group will be compared by Wilcoxon tests on repeated series.
- The improvement of the quality of life will be described through the IFC-specific Lymph Questionnaire by means of means, standard deviations and 95% confidence intervals and compared between the groups by a two-factor repeated time analysis of variance with interaction measurement. A Student's t-test will compare their variations between the two groups. The evolutions within each group will be compared by t-tests on repeated series.
- Their compliance with the Morisky score, the satisfaction of the patients in terms of efficiency and wearing comfort, their opinion on the ease of use of the product (need of a third person, applications of pressure, continuation of his use, advice to third parties, comparison with possible previous treatments, ease of use) will be compared between groups by Chi2 test or by a Fisher test if the characteristics of the distributions require it.
- The frequency and nature of adverse events will be described in terms of numbers and frequencies and compared between groups by Chi2 tests or Fisher tests if required by distribution conditions.
- The evolution of the quality of life of the patients will be described by numbers, percentages and 95% confidence interval and compared between groups by Wilcoxon rank tests. The evolutions within each group will be compared by Wilcoxon tests on repeated series.
- The frequency of those who use nurses or caregivers will be described by numbers, percentages, and 95% confidence intervals and will be compared between groups by Chi2 tests or Fisher tests if the characteristics of the distributions required it. The average number of nurse visits and its standard deviation will be calculated and compared between groups by Student's t tests. Its economic impact will be quantified by mean and standard deviation and compared by Student t tests on repeated series.
- The sociodemographic and clinical factors of patients likely to influence their adhesion, their satisfaction and the maintenance of the effect on lymphedema will be studied by logistic regression analyzes in order to identify those having a significant action after adjustments on the socio-demographic and clinics characteristic of the patients.

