2.2. SECONDARY OBJECTIVES

The secondary objectives are:

- To compare, on the 5th day of the reduction phase, the reduction in the volume of lymphatic edema of the upper limb obtained under the effect of the night and day wearing of the circaid® compression system and the night and day wearing of short lengthening bands such as recommended by the HAS.
- To compare, at the 90th day of the maintenance phase, the reduction in the volume of lymphatic edema maintained by the wearing of a compression sleeve during the day associated with the circaid® compression system at night and the wearing of a compression sleeve during the day associated with a possible wearing at night.
- To compare, at the 5th day of the reduction phase, at the 30th day of the initial maintenance phase and at the 90th day of the maintenance phase:
 - the physicians' opinions on lymphedema-induced discomfort improvement through the CGII (Clinical Global Improvement Impression);
 - the patients' opinions on lymphedema-induced discomfort improvement through the PGII (Patient Global Improvement Impression).
- To compare, at the 30th day of the initial maintenance phase and at the 90th day of the maintenance phase:
 - the adherence of patients to the wearing of their maintenance treatment;
 - the satisfaction and the wearing comfort experienced by the patients;
 - the patients' opinions on the ease of use of the product: the need for a third party, applications of pressure, the need for nurses or caregivers.
- To compare the tolerance of the different products at different phases of reduction and maintenance.

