9. STUDY COURSE

Following the meeting with CNEDIMTS (HAS), three observation periods were defined with the following products:

- D1 to D5: intensive hospital treatment performed by the night and day wearing of the circaid® compression system versus the night and day wearing of short stretching tapes.
- B. DD (Day of discharge from the hospital) to DD +30: ambulatory initial maintenance phase carried out by the wearing of a compression sleeve on the day associated with the nighttime compression system circaid® versus wearing a compression sleeve on the day associated with a possible treatment at night, as recommended by HAS.
- C. DD + 31 to DD + 90: ambulatory maintenance phase carried out by the wearing of a compression sleeve on the day associated with the nighttime circaid® compression system versus the wearing of a compression sleeve on the day associated with possible treatment at night.

Study design:

The study therefore includes four medical follow-up visits on day 0 (D0), day 5 (D5) (+/- 1 day), day of discharge (DD) + 30 days (+/- 5 days) and DD + 90 days (+/- 10 days), followed by self-questionnaire during the maintenance phase between DD and DD + 90, DD designating the day of discharge from the hospital at the end of the intensive reduction phase.

At D0, the doctor:

- collects the informed written consent of the patient after having duly informed her;
- collects its socio-demographic characteristics: age, occupation;
- collects the characteristics of its lymphedema: origin, date of onset, stage of edema according to the classification of the international society of lymphology, laterality of edema, volume of the arm with lymphedema, and volume of lymphedema compared to contralateral arm;

- collects the quality of life measured by the Lymph IFC specific questionnaire;
- implements decongestive treatment with the product defined by randomization.

At D5 (+/- 1 day), the doctor:

- collects the characteristics of lymphedema: stage of edema according to the classification of the international society of lymphology, volume of the arm with lymphedema, and volume of lymphedema compared to the contralateral arm;
- completes the PGII and CGII;
- records patient satisfaction in terms of efficiency and comfort of wearing measured on Likert scales in 5 classes;
- collects the occurrence of adverse events and their imputability to the products under study according to the materiovigilance;

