13.2. PROTOCOL DEVIATIONS AND ANALYSIS PLAN

All cases of deviations from the protocol will be managed according to CEN Biotech's Standard Operating Procedures.

A detailed statistical analysis plan, based mainly on this paragraph of the study protocol, and in accordance with CEN Biotech statistical procedures, will be developed. This analysis plan will be validated by the Medical Director of medi France.

A data validation plan will first focus on defining a position when considering protocol deviations and thus define the analysis populations (Intent to Treat and Per Protocol). The analysis plan will specifically identify the statistical tests, analysis procedures, treatment of missing data considered, and the primary and secondary endpoints that will be used.

Will be considered as major deviations (patient excluded from per protocol analysis) wrong inclusions (non-compliance with the inclusion criteria and non-inclusion) and the absence of data concerning the main criterion of analysis. All other cases will be considered *a priori* as minor deviations.

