13.4. STATISTICAL METHODS

13.4.1. Description of the population and comparability of groups at inclusion

The sociodemographic characteristics and the characteristics of their lymphedema (origin, date of onset, stage of edema according to the classification of the international society of lymphology, laterality of the edema, volume of the arm with lymphedema, and volume of lymphedema compared to contralateral arm) will be compared between groups by Chi2 tests for qualitative variables and by Student's t-tests for quantitative variables, or their non-parametric equivalents if the characteristics of distributions require it.

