13.4.2. Study of the main objective

The frequency of patients whose lymphedema volume reduction is at least 20% of the initial volume is described by numbers, frequencies, 95% confidence intervals and compared between groups by a Chi2 test at DD + 30.

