13.4.4. Intermediate analysis

Considering that the study is an open label study, an interim analysis may be conducted during the study when at least 50% of the initial enrollment has completed the study.

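### The continuous lymphedema-volume ANOVA in 13.4.3 names no D0 volume covariate, so its treatment main effect and any visit difference it gives are less precise than the collected data allow

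*Combined protocol and SAP*

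**What the plan says.** The first bullet of 13.4.3 specifies "repeated-time analysis of variance with two time factors and treatment with interaction on D5, DD + 30 and DD + 90". I read this as two factors, time and treatment, with their interaction, on three post-treatment visits. D0 is not a time level and no covariate is named. The bullet speaks of the evolution of the volume and does not say whether the outcome is raw volume, absolute change from D0 or percentage change.

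Section 9 lists, among the items collected at D0, the "volume of lymphedema compared to contralateral arm". The plan uses the D0 value in three other places: the comparability tests at inclusion (13.4.1), the reference for the responder criterion, a "lymphedema volume reduction is at least 20% of the initial volume" (13.4.2 and 13.4.3, second bullet), and the starting point for the share of day-5 benefit kept at DD+90 (13.4.3, third bullet).

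Two secondary objectives in 2.2 concern volume at a named visit: "To compare, on the 5th day of the reduction phase, the reduction in the volume of lymphatic edema of the upper limb" and "To compare, at the 90th day of the maintenance phase, the reduction in the volume of lymphatic edema". The second bullet of 13.4.3 tests the 20% responder frequency by Chi2 at those same two time points.

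Section 13.2 announces a detailed analysis plan, based mainly on section 13, which is not among the documents: "The analysis plan will specifically identify the statistical tests, analysis procedures, treatment of missing data considered".

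**The concern.** Volume before treatment is likely to predict volume after it. A model that leaves D0 volume out keeps that predictable variation in the error of the between-arm comparison. The comparability test in 13.4.1 can show a chance D0 difference but does not remove it from the estimate. The regressions at the end of 13.4.3 are logistic and look for factors behind adherence, satisfaction and maintenance of effect; they give no adjusted difference in volume.

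The first bullet is the only planned between-arm analysis of post-D0 volume on its continuous scale. What is at stake is the precision of that supporting analysis, when the data that would sharpen it are already in hand.

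**Working it through.** **Plan's own figure.** Section 13.1 assumes 75% against 50%, two-sided alpha 0.05 and 80% power. The pooled proportion is 0.625, so n = [1.96 × √(2 × 0.625 × 0.375) + 0.8416 × √(0.75 × 0.25 + 0.5 × 0.5)]² / 0.25² = (1.342 + 0.557)² / 0.0625 = 57.7, or 58 per group. This reproduces the plan. I use 58 per group at each visit as an illustration.

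**Assumptions.** The documents give no SD or correlation. In the main case the SD is 1 at every visit and every pair among D0, D5, DD+30 and DD+90 has correlation ρ.

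**Single visit.** The variance of the between-arm difference is (2/58) × v, and the 95% half-width is 1.96 × √(2v/58), in SD units.
- Raw volume: v = 1
- Change from D0: v = 2(1 − ρ)
- D0 as covariate: v = 1 − ρ²

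| ρ | v raw | v change | v adjusted | cut vs raw | cut vs change | half-width raw / change / adjusted |
|---|---|---|---|---|---|---|
| 0.3 | 1 | 1.40 | 0.91 | 9% | 35% | 0.364 / 0.431 / 0.347 |
| 0.5 | 1 | 1.00 | 0.75 | 25% | 25% | 0.364 / 0.364 / 0.315 |
| 0.7 | 1 | 0.60 | 0.51 | 49% | 15% | 0.364 / 0.282 / 0.260 |
| 0.8 | 1 | 0.40 | 0.36 | 64% | 10% | 0.364 / 0.230 / 0.218 |
| 0.9 | 1 | 0.20 | 0.19 | 81% | 5% | 0.364 / 0.163 / 0.159 |

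**Treatment main effect (mean of three visits).** Write m = (1 + 2ρ)/3. Raw v = m, change v = m + 1 − 2ρ, adjusted v = m − ρ². For ρ = 0.5, 0.7, 0.8:
- raw: 0.667, 0.800, 0.867
- change: 0.667, 0.400, 0.267
- adjusted: 0.417, 0.310, 0.227

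The cuts are 37.5%, 61%, 74% against raw and 37.5%, 22.5%, 15% against change.

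**Interaction, taken as the DD+90 minus D5 contrast.** D0 cancels from this contrast, so raw and change give the same v. Adjustment subtracts (r₉₀ − r₅)², where r₉₀ and r₅ are the correlations of D0 with those visits.
- Equal correlation: r₉₀ = r₅, so the cut is 0%.
- AR(1) with 0.7, visits treated as equally spaced: v = 2(1 − 0.49) = 1.020, less (0.343 − 0.7)² = 0.127, gives 0.893, a cut of 12.5%.
- Correlations D0–D5 0.9, D0–DD+90 0.4, D5–DD+90 0.5: v = 1.00 − (0.4 − 0.9)² = 0.75, a cut of 25%. The determinant is 1 + 0.36 − 0.81 − 0.16 − 0.25 = 0.14, so the pattern is possible.

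**Other structures, single visit.** Under AR(1) 0.7 the cuts at D5, DD+30 and DD+90 are 49%, 24%, 12% against raw and 15%, 25.5%, 33% against change. With follow-up SD 0.8 of D0 SD and equal correlation 0.7, raw v = 0.640, change v = 0.640 + 1 − 2 × 0.7 × 0.8 = 0.520 and adjusted v = 0.640 × 0.51 = 0.326. The cuts are 49% and 37%.

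**Chance imbalance.** The D0 difference between arms has variance 2/58 (SE 0.186 SD) and shifts the raw contrast by ρ times itself. At ρ = 0.7 that contributes 0.49 × 2/58, exactly the gap between v = 1 and v = 0.51. For change the shift is −(1 − ρ) times the difference, contributing 0.09 × 2/58, exactly the gap between 0.60 and 0.51. It is the same loss, not a further one.

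**Validity.** In 6,000 simulated trials per setting with no treatment effect and complete data, the type I error of the unadjusted raw-volume main-effect test was 0.049 (ρ 0.5) and 0.047 (ρ 0.9). With a true effect of −0.40 SD its mean estimate was about −0.40.

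**The case against.** The strongest reply is that the text leaves the outcome scale open. If evolution means change from D0, the model already uses D0 by subtraction, and it would be wrong to say that it ignores the baseline. That stands, and it is why the point is limited to the missing covariate. It does not remove the precision loss, since adjustment beats change as well, but it can make the gain small: at ρ 0.8 the half-width falls only from 0.230 to 0.218 SD. If a percentage scale is meant, these figures do not apply and the documents offer nothing from which to size the gain.

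Three further replies also stand. The 20% responder tests at D5 and DD+90 already serve the two volume objectives and refer to the initial volume. The first bullet promises no visit-specific difference or interval, so the plan's stated output is not shown to be too wide; the loss concerns the main effect and any visit difference taken from the model. And if evolution is read as the interaction, adjustment may gain nothing.

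The later plan may already name D0. But 13.2 says it will rest mainly on section 13, so the omission would probably carry over.

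A reader might also infer that the ANOVA is biased, that chance D0 imbalance makes it invalid, or that the primary result or trial size is in doubt. The documents support none of these. Section 4 describes a randomised trial, so the unadjusted standard error already allows for chance imbalance; the primary analysis is a separate Chi2 test, and 13.1 sizes the trial on that test alone.

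**Conclusion.** The point holds as a free improvement to a supporting analysis. The ANOVA in the first bullet of 13.4.3 is valid but names no D0 covariate, and its treatment main effect and any visit difference drawn from it lose precision on either the raw or the absolute-change scale. The direction is firm: adjustment is at least as precise as either, apart from a negligible cost in degrees of freedom. The size is not known, because it rests on assumed SDs and correlations. Over an equal correlation of 0.5 to 0.8 the single-visit gain is moderate to large against raw volume and modest against change. No general gain can be claimed for the interaction: it was zero, 12.5% and 25% in the three patterns tried. Validity here means under randomisation and complete data; missing visits and sphericity were not examined.

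**What to change.** In 13.4.3, first bullet, and in the later analysis plan:
- keep the repeated-measures model on D5, DD+30 and DD+90 with treatment, time and their interaction, and add D0 lymphedema volume and D0-by-time as covariates;
- do not enter D0 as a fourth time level. The arms do not differ at D0 in expectation, so a constant effect of −0.40 SD would be averaged to −0.40 × 3/4 = −0.30 SD in the main effect;
- state the outcome scale. With these D0 terms raw volume and absolute change give the same adjusted difference; a percentage scale would not;
- report the adjusted between-arm difference with its 95% CI at each visit, labelled secondary.

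Leave the responder analyses, the primary Chi2 test and the sample size unchanged.

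The cost is a few lines of wording and routine code in the SAS software already named in 13.4.5. The D0 terms use three parameters, one slope per visit. No new data and no new patients are needed.

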5.3. SAMPLE SIZE

The calculation performed with Nquery (see 13.1) shows that 136 patients are required (68 per group), which is increased to a total of 140 patients to take account patients lost of follow-up.

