- collects the quality of life measured by the Lymph IFC specific questionnaire;
- gives the patient a self-questionnaire on which she reports each week who has placed the contention device (herself, spouse, nurse), and the existence of an intolerance to the wearing of it;
- gives the patient, according to the randomization list, the products under study during the maintenance phase;
- provides a nursing prescription for the application of a possible treatment to the patients concerned.

At DD + 30 days (+/- 5 days), the doctor:

- collects the characteristics of lymphedema: stage of edema according to the classification of the international society of lymphology, volume of the arm with lymphedema, and volume of lymphedema compared to the contralateral arm;
- collects the PGII and CGII;
- collects the quality of life measured by the Lymph IFC specific questionnaire;
- records patient satisfaction in terms of efficiency and wearing comfort measured on Likert scales in 5 classes;
- collects the observance of the port during the initial maintenance phase by the adapted Morisky score;
- collects the occurrence of adverse events and their imputability to the products under study according to the materiovigilance;
- retrieves the self-questionnaire from the early maintenance period and gives the patient a self-questionnaire for the maintenance period where she reports on each week who apply the compression device (herself, spouse, nurse), and the existence of an intolerance to the wearing of it;
- provides a nursing prescription for the application of a possible treatment to the patients concerned;
- gives the patient, according to the randomization list, the products under study during the maintenance phase.

At DD + 90 days (+/- 10 days), the doctor:

- collects the characteristics of lymphedema: stage of edema according to the classification of the international society of lymphology, volume of the arm with lymphedema, and volume of lymphedema compared to the contralateral arm;
- collects the PGII and CGII;
- collects the quality of life measured by the Lymph IFC specific questionnaire;

- records patient satisfaction in terms of efficiency and wearing comfort measured on Likert scales in 5 classes;
- collects the observance of the port during the long-term maintenance phase by the adapted Morisky score;
- collects the occurrence of adverse events and their imputability to the products under study according to the materiovigilance;

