13.1. SAMPLE SIZE

The sample size is based on the assumption that at the end of the maintenance period, 3 out of 4 patients will have at least a 20% decrease in the volume of their lymphedema in the circaid® group versus 1 in 2 in the control group. At risk alpha = 0.05, in a two-sided Chi2 test with a power of 80%, the calculation performed with Nquery (see table below) shows that the number of patients required to highlight this difference is 58 patients per group. This number is increased by 15% to account for patients lost to follow-up or unusable records, i.e. 68 per group. These patients will be recruited by 5 centers on the basis of 28 patients per center. Two group χ^2 test of equal proportions (odds ratio = 1) (equal n's)

Test significance level, α	0,050
1 or 2 sided test?	2
Group 1 proportion, π_1	0,250
Group 2 proportion, π_2	0,500
Odds ratio, $\psi = \pi_2 (1 - \pi_1) / [\pi_1 (1 - \pi_2)]$	3,000
Power (%)	80
n per group	58

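### Quality of life: three between-arm analyses are listed, none is designated as main and none adjusts for the D0 score already collected; analysis of covariance would be a free gain in precision

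*Combined protocol and SAP*

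**What the plan says.** Section 9 (Study course) has the investigator record quality of life at D0: "collects the quality of life measured by the Lymph IFC specific questionnaire". The same item is in the visit lists for D5, DD+30 and DD+90, so every patient should have a pre-treatment score and three later ones.

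Section 13.4.3 (Studies of secondary objectives) then gives three between-arm analyses of this score:

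- a two-factor repeated-measures analysis of variance with interaction, with no time points listed;
- a t-test on change: "A Student's t-test will compare their variations between the two groups";
- in a separate, later bullet, Wilcoxon rank tests on how quality of life evolves.

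No order of priority is given, no main time point is named, and none of the three names the D0 score as a covariate. The only covariate-adjusted models in Section 13.4 are the logistic regressions on adherence, satisfaction and maintenance of effect. Section 13.4.1 does not include the D0 quality-of-life score among the characteristics compared at inclusion.

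Section 13.2 says that a detailed analysis plan will be developed, based mainly on Section 13 of the protocol.

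**The concern.** A t-test on change uses the baseline by subtracting it in full, which assumes that a one-point difference at D0 carries through as a one-point difference at follow-up. Questionnaire scores usually regress toward the mean, so the true within-arm slope is often below 1. The subtraction then adds noise, and a chance difference between arms at D0 is over-corrected. Analysis of covariance estimates the slope from the data instead.

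At stake is the precision of one secondary result. Section 1.2 says the device improves quality of life, and the trial is intended to support reimbursement in France, so the estimate will be read. With three analyses and none designated, there is also no set rule for which one the report should rely on if they disagree.

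**Working it through.** **Inputs from the documents.** There is no quality-of-life SD, target difference, correlation or power. The only sample-size calculation is in Section 13.1, for the binary primary endpoint: circaid® 75% ("3 out of 4 patients will have at least a 20% decrease in the volume of their lymphedema") against 50% in the control group, "in a two-sided Chi2 test with a power of 80" per cent, alpha 0.05.

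**The plan's own figure.** With pooled proportion 0.625:

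n = [1.960 × √(2 × 0.625 × 0.375) + 0.842 × √(0.75 × 0.25 + 0.50 × 0.50)]² / 0.25² = (1.342 + 0.557)² / 0.0625 ≈ 57.7, so 58 per group.

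This agrees with the protocol ("the number of patients required to highlight this difference is 58 patients per group"). Power at 58 per group is 80.2%. The 68 per group corresponds to 58 / 0.85 = 68.2. The primary calculation stands and is not touched by this point.

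**Change score against covariance adjustment, general case.** Let ρ be the within-arm correlation of D0 and follow-up scores and k = SD at D0 / SD at follow-up. In units of the follow-up variance:

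- change score: 1 + k² − 2ρk
- analysis of covariance: 1 − ρ²
- difference: (1 + k² − 2ρk) − (1 − ρ²) = (k − ρ)²

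The difference is never negative. It is zero only when k = ρ, which is when the slope ρ/k equals 1. So covariance adjustment costs at most one degree of freedom (113 instead of 114 at 58 per arm). The gain can vanish: at ρ = 0.7 and k = 0.7 the ratio is 0.51 / 0.51 = 1.

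**Equal SDs (assumption, k = 1).** The variance ratio becomes (1 − ρ²) / [2(1 − ρ)] = (1 + ρ)/2.

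**Power (second assumption: the change-score t-test has 80%).** Its standardised effect is then 1.960 + 0.842 = 2.802. With covariance adjustment it is 2.802 / √[(1 + ρ)/2], and power is Φ of that value minus 1.960.

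| ρ (assumed) | Variance ratio | CI width ratio | Standardised effect | Power | Gain (points) |
|---|---|---|---|---|---|
| 0.3 | 0.65 | 0.806 | 3.475 | 93.5% | 13.5 |
| 0.5 | 0.75 | 0.866 | 3.235 | 89.9% | 9.9 |
| 0.7 | 0.85 | 0.922 | 3.039 | 86.0% | 6.0 |
| 0.8 | 0.90 | 0.949 | 2.953 | 84.0% | 4.0 |
| 0.9 | 0.95 | 0.975 | 2.875 | 82.0% | 2.0 |

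The noncentral t distribution gives the same powers at 58 and at 68 per arm.

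**Sensitivity to the 80% anchor.** If the adjusted analysis is set at 80% instead, the t-test has 61.7% (ρ = 0.3), 67.9% (0.5), 73.3% (0.7) or 78.0% (0.9), a loss of 18.3 down to 2.0 points. For fixed effects of 0.3 to 0.5 SD at 58 per arm and ρ from 0.3 to 0.9, the gap runs from about 18 points (0.5 SD, ρ = 0.3: 62.4% against 80.6%) to about zero (0.5 SD, ρ = 0.9).

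**The repeated-measures ANOVA.** If D0 is one of its time levels, the interaction uses D0 as change, without a fitted slope. The group main effect would average in a visit before treatment, so a constant effect at three later visits would shrink to 3/4 of its size. If D0 is not a time level, baseline is ignored. Neither reading is covariate adjustment, and the text does not say which is meant.

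**The case against.** Several stronger readings are tempting, and the documents do not support them.

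- *The t-test is the only between-arm analysis of change.* It is not. The ANOVA stands in the sentence just before it, and the Wilcoxon tests come in a later bullet.
- *The plan loses a definite amount of power, for example 6 to 10 points.* That range needs ρ between 0.5 and 0.7, equal SDs at D0 and follow-up, and a t-test at exactly 80% power. None of these is stated for quality of life; the 80% in Section 13.1 belongs to the primary endpoint.
- *The change score is inefficient whenever ρ is below 1.* Not in general. The condition is that the slope ρ/k differs from 1.
- *The comparison is biased or invalid.* Under randomisation the t-test on change is unbiased and keeps its type I error. Over-correction arises only conditionally on a chance D0 difference.
- *The ANOVA dilutes the effect.* That depends on D0 being a time level. The volume ANOVA in the same section uses D5, DD+30 and DD+90 only. If D0 is included, the interaction that the plan specifies is the natural treatment test, and it is not diluted in that way.

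Two further objections carry weight. Quality of life is a secondary criterion (Section 8.2), is absent from the secondary objectives in Section 2.2, and does not drive the sample size. And Section 13.2 leaves the detailed tests to a later analysis plan. The first limits the importance of the point. The second does not remove it: a specific test is already written, the later plan is to be based mainly on this text, and a better test exists for data already collected.

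**Conclusion.** The point holds as a free improvement. What the documents establish is that there are three between-arm analyses of the Lymph score, with none designated as main and none adjusted for D0. The direction is firm: covariance adjustment is never less precise than the change score beyond one degree of freedom.

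The size is not established. Assuming equal SDs and a t-test at 80% power, the gain is about 13.5 points at a correlation of 0.3, falling to about 2 points at 0.9. It goes to none if the within-arm slope is near 1. Other anchors give a range from about 0 to 18 points.

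The primary analysis, the 58 per group and the validity of the planned tests are unaffected.

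**What to change.** In Section 13.4.3 and the detailed analysis plan:

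- Replace the t-test on variations by an analysis of covariance of the Lymph score on arm and D0 score. Make DD+30 the main time point, in line with the primary criterion, with D5 and DD+90 supportive. Report the adjusted difference with its 95% CI. If change is the preferred outcome for presentation, modelling change on arm and D0 score gives the same adjusted difference.
- In the repeated-measures model, list D5, DD+30 and DD+90 as the outcome visits and enter the D0 score as a covariate.
- State that the analysis of covariance is the main quality-of-life comparison and label the Wilcoxon analysis supportive.

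The cost is a change of wording, made before the data are analysed. It needs no extra patients, visits or measurements, because the D0 score is already collected.
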